6.3 Product Allocation and Blinding

6.3.1 Methods of Assigning Subjects to Product Arms

At the end of the Baseline period enrolled subjects will be randomized using an interactive web and voice response system (IxRS) on Day -1 at any time during the day. Subjects will be informed of their randomized study arm in the morning of Day 1, prior to 06:30 AM (the start of the exposure period). Subjects will be randomized to one of the 2 study arms: CHTP 1.2 or CC in a 2:1 ratio.

Stratified randomization will be conducted by sex and by average daily CC consumption over the last 6 weeks prior to Admission as self-reported (smoking 10 to 19 CC/day vs. > 19 CC/day). In each arm, each sex and each of the smoking strata will have a quota applied to ensure they represent at least 40% of the population.

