12.5.1.1 Primary endpoints

COHb in blood, and urinary concentrations adjusted for creatinine of MHBMA, 3-HPMA and S-PMA, and total NNAL will be summarized on the log-scale as detailed in **Section 12.1.3 “Descriptive Statistics”**. Distributions will be tested for log-normality and appropriate non-parametric methods will be used in case of non-lognormally distributed data as described in **12.1 General Considerations**.

The values and percent changes from baseline in the concentration adjusted for creatinine of MHBMA, 3-HPMA, S-PMA and total NNAL will be listed and summarized along with the COHb concentrations and percent changes from baseline (Tables 15.2.3.3-7.1, 15.2.3.3-7.2 and Listing 15.3.3.1). This will also be summarized by sex, by average cigarette consumption over the previous 6 weeks prior to admission and by product use category (Tables 15.2.3.3-7.1.1, 15.2.3.3-7.1.2 and 15.2.3.3-7.1.3).

The log-transformed data will be analyzed by means of an ANCOVA (on Day 5 for COHb, MHBMA, 3-HPMA and S-PMA and Day 90 Visit for total NNAL) using arm as covariate adjusting for sex and average cigarette consumption over the previous 6 weeks prior to admission, and log-transformed baseline value of endpoint.

The SAS code to be used for COHb in blood, and urinary concentrations adjusted for creatinine of MHBMA, 3-HPMA and S-PMA on Day 5 and total NNAL adjusted for creatinine at Day 90 Visit is shown below:

```
Proc mixed data=_data_ ;  
Class arm sex cigarette_cons ;  
Model log (Value) = log (baseline) sex cigarette_cons arm ;  
Lsmeans arm / pdiff =control('CC') alpha=0.05 cl ;  
Run ;
```

The least squares (LS) means and estimate of the difference along with its 95% CI will be back-transformed before presenting in the tables. The geometric LS means for each arm along with the reduction (i.e: 100% - ratio of CHTP 1.2 : CC (%)) and 95% CI will be presented in the tables (Table 15.2.3.1).

In addition line graphs will be produced for arm geometric means (and 95% CI) over all timepoints for COHb in blood, and urinary concentrations adjusted for creatinine of MHBMA, 3-HPMA, S-PMA and total NNAL (Figure 15.1.1.1-5).

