12.5.2.5 Assessment of Cough

Cough questionnaire is assessed on a daily basis from Day -2 to Day 6, at Day 30 Visit, Day 60 Visit and Day 90 Visit. Questionnaire details are reported in Section 7.4.7 “Cough Assessment”.

The number and % of subjects reporting cough will be summarized over the study by study arm for the safety and PP population and by product use pattern categories for the Safety population. The responses to the individual items, including the VAS evaluating the level of cough bother and 3 Likert scales measuring the intensity, the frequency of cough and the amount of sputum production will be summarized over the study by study arm for all subjects who filled in the questionnaire and reported cough (Table 15.2.4.22.X). If a subject has answered question more than once then the most severe intensity/frequency/sputum production is presented for the “over the study” tables. No assumptions will be made in case of missing intensity/frequency/sputum production. The number and % of subjects reporting cough, The responses to the individual items, including the VAS evaluating the level of cough bother and 3 Likert scales measuring the intensity, the frequency of cough and the amount of sputum production will be listed and summarized on each day by study arm and by product use pattern categories (Table 15.2.4.23.X and Table 15.2.4.24.X) for all subjects who filled in the questionnaire and reported cough. The answers to the open question(s) related to any other important observation will be listed (Listing 15.3.4.4).

In addition, a GEE model will be used to evaluate the differences between proportions (with 2-sided p-values) and 95% CI for the need to cough between CHTP 1.2-use and CC-use at

V2, V3 and V4 in the per protocol population and in the safety population (Table 15.2.4.26.X). The model will include terms for visit, baseline level and its interaction with visit, sex, and product use pattern category and its interaction with visit. The point estimate and 95% CI of proportions and the Odds Ratios (with 2-sided p-values) will also be produced for CHTP 1.2 (CHTP 1.2 arm) versus CC (CC arm) and for CHTP 1.2 Dual-use (CHTP 1.2 arm) versus CC-use (CC arm). The interaction term will be removed if $p > 0.1$.

The SAS code to be used is shown below:

```
proc glimmix data = _data_ ;  
  class trtan avisit sex usubjid;  
  model aval = base base*visit pattern avisit sex  
  trtan*pattern/dist = binomial link=logit solution;  

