  random _residual_/subject=usubjid type = un;  
  lsmeans trtan*avisit ;  
run;
```

For the confinement period, a similar model will be run, replacing the product use category with the treatment arm (Table 15.2.4.25.X).

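### The two cough models in SAP 12.5.2.5 omit the daily-cigarette stratum that every other inferential model carries; adding it is a nearly free improvement, and it matters mainly for the ambulatory model

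*SAP*

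**What the plan says.** SAP 6.3.1 sets the design: "Stratified randomization will be conducted by sex and by average daily CC consumption over the last 6 weeks prior to Admission as self-reported", split at 10–19 versus >19 per day. A quota holds each smoking stratum to at least 40% of each arm.

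For the need to cough at Visits 2, 3 and 4, SAP 12.5.2.5 specifies a GEE in the per-protocol and safety populations. On its covariates it says: "The model will include terms for visit, baseline level and its interaction with visit, sex, and product use pattern category", and the category also interacts with visit. The printed statement agrees about the missing stratum: "model aval = base base*visit pattern avisit sex", followed on the next line by an arm-by-pattern term. Consumption is also absent from the CLASS list. The requested contrasts set CHTP 1.2 users, and dual users, within the CHTP 1.2 arm against the CC arm. For the earlier period, "For the confinement period, a similar model will be run, replacing the product use category with the treatment arm", so that model lacks the stratum too.

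The primary analysis in SAP 12.5.1.1 does carry it; its code reads "Class arm sex cigarette_cons".

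**The concern.** A factor used to stratify randomisation would normally appear in the analysis model. This SAP follows that practice everywhere except cough and gives no reason for the exception.

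The ambulatory model is where it could matter. Under SAP 6.3.3.1 and Table 7, use categories come from what CHTP 1.2 subjects report using after randomisation. A subset of one arm is then compared with the other arm, and stratified randomisation no longer guarantees that the two groups have the same mix of lighter and heavier smokers. If lighter smokers are over-represented among CHTP 1.2 users and cough less for reasons that baseline cough does not capture, part of that difference would be credited to the product. Cough is both a secondary endpoint and a safety variable, so the estimate is likely to be read.

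**Working it through.** **1. Audit of model terms.** The plan gives no cough rate, power or sample size, so there is no planned figure to reproduce. I checked each inferential model in SAP 12.5 for a consumption term.

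- Named in text or code (10 groups): primary biomarkers (12.5.1.1); exhaled CO, with Day 90 COHb under the same model (12.5.2.1.1); NEQ (12.5.2.1.3); CYP1A2 (12.5.2.3); spirometry (12.5.2.4); oxidative stress (12.5.2.7); QSU-brief (12.5.3.1.1); mCEQ (12.5.3.1.2); FTND (12.5.3.1.4); CYP2A6 (12.5.3.2).
- Present through cross-referenced code (3 groups): secondary urinary biomarkers (12.5.2.1.2); nicotine and cotinine (12.5.2.2); cardiovascular endpoints (12.5.2.6).
- Absent: both cough models (12.5.2.5).

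ITUQ, Prochaska, the Ames test and the other safety outputs are descriptive. The count is 13 of 13 with the term and 2 of 2 without.

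**2. How bias could arise, ignoring baseline cough.** Take no product effect. Let *h* be the share of >19/day smokers, *p0* and *p1* the cough risks in lighter and heavier smokers, and *uL* and *uH* the proportions of each stratum entering the CHTP 1.2 category. Only the range of *h* (0.4–0.6) follows from the documents; the rest is assumed.

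- Heavier share among users = h·uH / (h·uH + (1−h)·uL)
- Cough risk in a group = (1 − heavier share)·p0 + heavier share·p1

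With h = 0.5, p0 = 0.20 and a heavier:lighter odds ratio of 2, the heavier odds are 0.25 × 2 = 0.5, so p1 = 0.333.

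- CC arm: 0.5 × 0.20 + 0.5 × 0.333 = 0.267.
- Users at 60%/40% uptake: heavier share 0.4, risk 0.253. Odds ratio = (0.253/0.747)/(0.267/0.733) = 0.93.
- Users at 70%/30%: heavier share 0.3, risk 0.240, odds ratio 0.87.
- Users at 50%/50%: odds ratio 1.00.

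Over h = 0.4–0.6 and stratum odds ratios of 1.5–3, the range is 0.96 to 0.90 at 60/40 and 0.93 to 0.80 at 70/30. This overstates the problem, because the SAP model adjusts for baseline cough.

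**3. With baseline cough in the model.** One visit was simulated with no product effect, a between-subject SD of 1.5 on the logit scale (assumed) and 600,000 subjects per scenario. Fitted CHTP 1.2:CC odds ratios, without / with the stratum:

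| Stratum odds ratio | Uptake 60%/40% | Uptake 70%/30% |
|---|---|---|
| 1.5 | 0.983 / 1.004 | 0.965 / 1.012 |
| 2 | 0.960 / 0.997 | 0.936 / 1.012 |
| 3 | 0.937 / 0.993 | 0.883 / 0.999 |
| 4 | 0.923 / 0.995 | 0.860 / 1.000 |

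The return to about 1 is by construction, since the stratum is the only confounder simulated. A repeat with an assumed intercept of −1.4 gave about 0.97 to 0.93 and 0.95 to 0.86, and no bias at equal uptake.

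**4. Against the trial's own precision.** The same set-up was run at trial size (randomised 80 and 40; stratum odds ratio 2–4; assumed overall cough rates 24–45%; 3,000 simulations per scenario). The median log odds ratio was −0.02 to −0.17, against a standard error of 0.49–0.58: about 0.04 to 0.33 standard errors. Two-sided 5% rejection was 4.0–5.5% without the stratum and 3.9–5.2% with it.

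**5. Confinement model.** Arms are randomised within strata, so there is no confounding. At 80 versus 40 with an assumed product log odds ratio of −1.6, power without and with the stratum was 81.4% and 81.9% (stratum odds ratio 2), and 78.9% and 79.6% (stratum odds ratio 4). The gains are 0.5 and 0.7 points. With 1,500 simulations, each power estimate has a Monte Carlo error of √(0.81 × 0.19/1500) ≈ 1.0 point.

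**The case against.** The strongest reply is that nothing in the documents shows confounding. Consumption would have to predict use category, and also predict cough after allowing for baseline cough and sex, which are already in the model. The plan has no data on either link. The use category is a proportion of total product use, so it has no built-in tie to cigarettes per day. The per-protocol adherence limits in SAP Table 12 are absolute CC counts, so a tie is more plausible there, but that too is inference. This objection stands: a reader might infer that baseline smoking is a confounder, or that the cough result will favour CHTP 1.2, and the documents support neither statement.

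It is also fair that the illustrated bias is small beside the standard error, and that the simulations cover one visit instead of the planned repeated-measures GEE. One added term also leaves selection through dependence, product preference or tolerability untouched. All of this stands.

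A reader might further infer an undeclared departure from the protocol, because SAP section 9 does not mention the omission. That does not follow. Section 9 records changes from protocol-specified analyses, and the protocol specifies no inferential cough model; its covariate list in section 12.4.4 is for biomarkers of exposure.

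None of these points gives a reason for leaving the stratum out.

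**Conclusion.** The omission is certain: text and code agree, and these are the only inferential arm or product comparisons in the SAP without the stratum. Its consequence is limited. In confinement the model merely fails to reflect the stratified design, with negligible loss of precision. In the ambulatory model baseline consumption is a potential confounder. An odds ratio of about 0.98 to 0.86 where the truth is 1 requires uneven uptake (60/40 to 70/30) and a stratum odds ratio for cough of 1.5 to 4, all assumed. That is unlikely to change a cough conclusion in a trial of this size. The primary analysis is unaffected, since it already adjusts for both stratification factors. This is an optional improvement, worth making because it costs so little.

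**What to change.** In SAP 12.5.2.5, add average daily CC consumption at Admission (10–19 versus >19) to the stated terms of both cough models, and put cigarette_cons in the CLASS and MODEL statements, as in 12.5.1.1.

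Make the printed code match the text in the same edit. At present it has an arm-by-pattern term where the text calls for category by visit, uses both visit and avisit, leaves pattern out of CLASS, and requests least squares means for an arm-by-visit effect that is not in the MODEL statement.

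State beside the ambulatory results that use groups are self-selected and that the added term does not correct for other differences between them. The by-arm confinement model and the by-arm summaries remain the comparisons that follow the randomised arms.

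The cost is one covariate, already collected and already used in the other models, plus the code clean-up. If the SAP can no longer be amended before database lock, run the adjusted models as additional analyses and describe them in the study report, as SAP section 3 provides.

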12.5.2.6 Cardiovascular Risk Endpoints

The following cardiovascular risk endpoints will be assessed:

- Systolic and Diastolic Blood Pressure at baseline, Day 6, Day 30 Visit, Day 60 Visit and Day 90 Visit.
- High sensitive C-reactive protein (hs-CRP), blood glucose, myeloperoxidase (MPO), low density lipoprotein (LDL), high density lipoprotein (HDL), triglycerides (TG), and total cholesterol (TC) in serum at Baseline, Day 30 Visit, Day 60 Visit, and Day 90 Visit
- Fibrinogen, homocysteine in plasma at baseline, Day 30 Visit, Day 60 Visit, and Day 90 Visit
- Hemoglobin A1c (HbA1c) in blood at Day -1, and Day 90 Visit
- Apolipoprotein A1 (Apo A1) and apolipoprotein B (Apo B) in serum at baseline, and Day 90 Visit
- Soluble inter-cellular adhesion molecule-1 (sICAM-1) in serum at baseline, Day 6, Day 30 Visit, Day 60 Visit, and Day 90 Visit
- White blood cell (WBC) and platelet counts in blood at baseline, Day 6, Day 30 Visit, Day 60 Visit, and Day 90 Visit
- 11-dehydro-thromboxane B2 (11-DTX-B2) in 24-hour urine at baseline, Day 5, Day 30 Visit, Day 60 Visit, and Day 90 Visit (expressed as concentration adjusted for creatinine)
- Body Weight and Waist Circumference at baseline and Day 90 Visit.

It is assumed that the following cardiovascular parameters can be analyzed in natural scale: MPO, Apo A1, Apo B, LDL-C, HbA1c, WBC count, Systolic and Diastolic Blood Pressure, weight, and waist circumference.

It is assumed that the following cardiovascular parameters can be analyzed in the logarithmic scale: hs-CRP, blood glucose, TG, TC, fibrinogen, homocysteine, sICAM-1, platelets and 11-DTX-B2.

These clinical risk endpoints will be summarized and listed by arm, subject, parameter and time point, together with numerical changes or percent changes (as applicable; see section “**12.1.3 Descriptive Statistics**”) from baseline (Listing 15.3.4.5). The number and percentage of subjects with normal results, high/low results and abnormal clinical result (as defined by PI comment) and with shift in normality or toxicity if applicable will be tabulated.

The actual values, along with the change from baseline for MPO, Apo A1, Apo B, LDL-C, HbA1c, WBC, Systolic and Diastolic Blood Pressure, weight, and waist circumference will be summarized (Table 15.2.4.26).

The actual values, along with the percent change from baseline for glucose, hs-CRP, TG, TC, homocysteine, fibrinogen, sICAM-1, platelets, 11-DTX-B2 will be summarized (Table 15.2.4.27).

The profiles of the means (geometric for parameters analyzed in logarithmic scale and arithmetic for parameters analysed in natural scale) per time point will be produced for all endpoints except HbA1c, Apo A1, Apo B, weight and waist circumference which are only assessed at baseline and Day 90 Visit (Figure 15.1.2.29–46).

For all endpoints, an ANCOVA model will be used on Day 5 and on the Day 90 Visit (as applicable). The SAS code will be the same as described in Section 12.5.1.1 “**Primary endpoints**”; except that there will only be a log transformation of the endpoints as specified above. For HbA1c, Apo A1, Apo B, waist circumference and body weight; the analysis will compare the Day 90 Visit values.

As applicable, geometric LS means for each arm along with the % reduction (100% - CHTP 1.2 : CC Ratio (%)) for hs-CRP, blood glucose, TG, TC, fibrinogen, homocysteine, sICAM-1, platelets and 11-DTX-B2 or the arithmetic LS means along with the difference (CHTP 1.2 - CC) for the other endpoints; per timepoint with 95% CI will be presented in the table. (Table 15.2.4.28).

All figures, summaries and analyses will be performed on the Per Protocol Populations.

If applicable, the tables with descriptive statistics will be repeated for the group of subjects who attempt to quit (see section “**10.7 Quitters Population**”).

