- Systolic and diastolic blood pressure on Day 6, at Visit 2, Visit 3, and Visit 4
 - High sensitive C-reactive protein (hs-CRP), blood glucose, myeloperoxidase (MPO), low density lipoprotein (LDL), high density lipoprotein (HDL), triglycerides (TG), and total cholesterol (TC) in serum at Visit 2, Visit 3, and Visit 4
 - Fibrinogen, homocysteine in plasma at Visit 2, Visit 3, and Visit 4
 - Hemoglobin A1c (HbA1c) in blood at Visit 4
 - Apolipoprotein A1 (Apo A1) and apolipoprotein B (Apo B) in serum at Visit 4
 - Soluble inter-cellular adhesion molecule-1 (sICAM-1) in serum on Day 6, at Visit 2, Visit 3, and Visit 4
 - White blood cell (WBC) and platelet counts in blood on Day 6, at Visit 2, Visit 3, and Visit 4
 - 11-dehydro-thromboxane B2 (11-DTX-B2) in 24-hour urine on Day 5, at Visit 2, Visit 3, and Visit 4 (expressed as concentration adjusted for creatinine)
 - Body weight and waist circumference at Visit 4
7. To evaluate the changes in levels of selected clinical risk endpoints related to oxidative stress over the entire exposure period in smokers switching from CC to CHTP 1.2 as compared to smokers continuing to use CC

Endpoints (Day 5 to Visit 4):

- Epi-prostaglandin F2 α (8-epi-PGF2 α) in 24-hour urine on Day 5, at Visit 2, Visit 3, and Visit 4 (expressed as concentration adjusted for creatinine)
- Ratio 8-epi-prostaglandin F2 α (8-epi-PGF2 α) to prostaglandin F2 α (PGF2 α) in plasma on Day 5 and at Visit 4

Confidentiality Statement

Data and information contained in this document are considered to constitute trade secrets and confidential commercial information, and the legal protections provided to such trade secrets and confidential information are hereby claimed under the provisions of applicable law. No part of this document may be publicly disclosed without the written consent of Philip Morris Products S.A.

- 8-Hydroxy-2'-deoxyguanosine (8-OHdG) in 24-hour urine on Day 5, at Visit 2, Visit 3, and Visit 4 (expressed as concentration adjusted for creatinine)
- 4-Hydroxy-2-nonenal (4-HNE) in serum on Day 5 and at Visit 4 ^a
- Total anti-oxidant capacity (TAC) in serum on Day 5 and at Visit 4

^a Samples for 4-HNE analysis have been collected but will not be analyzed due to the failure to develop a selective and quantitative assay.

8. To describe the change in cytochrome P450 1A2 (CYP1A2) enzymatic activity in smokers switching from CC to the CHTP 1.2 as compared to smokers continuing to use CC

Endpoint (Day 5 and Visit 4):

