Abbreviations: AE = Adverse event; BoExp = Biomarker (s) of exposure; CAF = Caffein; CC = Combustible cigarette(s); CHTP 1.2 = Carbon Heated Tobacco Product 1.2; CO = Carbon monoxide; COHb = Carboxyhemoglobin; IP = Investigational product; MCEQ = Modified Cigarette Evaluation Questionnaire; QSU–brief = Questionnaire of Smoking Urges (brief version); SAE = Serious adverse event; VAS = Visual Analogue Scale

Table 14 shows the assessments that will be performed on Day 6, prior to Discharge from the study unit.

Table 14 Time Schedule – Day of Discharge (Day 6)

Time	Blood Sample	Procedures	Additional Information
Start of Procedure		Day 6	
6:30 AM		Start of use of IPs	
During the visit		AE/SAE recording	
During the visit		Concomitant medications	
		End of 24-hour urine sample collection for Day 5	The urine is collected for 24 hours ±1 hour

Confidentiality Statement

Data and information contained in this document are considered to constitute trade secrets and confidential commercial information, and the legal protections provided to such trade secrets and confidential information are hereby claimed under the provisions of applicable law. No part of this document may be publicly disclosed without the written consent of Philip Morris Products S.A.

Time	Blood Sample	Procedures	Additional Information
Start of Procedure		Day 6	
		Urine sample to be taken from the 24-hour urine of Day 5	Aliquots from 24-hour urine will be collected according to Table A2 . Bio-banking for biomarkers (if additional consent is obtained)
06:29 AM ± 1.5 hour	√	Clinical laboratory parameters* (hematology, clinical chemistry), cardiovascular clinical risk endpoint: sICAM-1	After at least 10 hours of fasting * Blood glucose, TG, TC, WBC, platelet count from safety will be also evaluated as clinical risk endpoints
06:29 AM ± 1.5 hour	√	CYP2A6 activity in plasma	Has to be done prior to use of IPs
06:29 AM ± 1.5 h	√	Plasma nicotine and cotinine sample	Cotinine will be measured in the same assay as nicotine. No additional blood samples required
06:29 AM ± 1.5 hour		Spirometry pre- and post-bronchodilator (recording of FEV ₁ , FVC, FEV ₁ /FVC)	Has to be done prior to use of IPs At rest in sitting position for at least 15 minutes prior to pulmonary function testing In sitting position All post-bronchodilator spirometry testing will be performed 15-30 minutes post administration of salbutamol

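### The cardiovascular ANCOVA is set for Day 5, but blood pressure, sICAM-1, WBC and platelets are Day 6 endpoints, so the short-term comparison is either absent or on the wrong day

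*SAP*

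**What the plan says.** The analysis sentence in SAP 12.5.2.6 reads: "For all endpoints, an ANCOVA model will be used on Day 5 and on the Day 90 Visit (as applicable". It then refers to the model code for the primary endpoints. No other time point is given for a cardiovascular ANCOVA.

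The endpoint list at the top of the same section gives the assessment days. Blood pressure is placed at Day 6 in confinement: "Systolic and Diastolic Blood Pressure at baseline, Day 6, Day 30 Visit, Day 60 Visit and Day 90 Visit". The sICAM-1 entry follows the same pattern, as do the two blood counts, whose entry is: "White blood cell (WBC) and platelet counts in blood at baseline, Day 6, Day 30 Visit, Day 60 Visit, and Day 90 Visit". The one urinary marker in the list differs, because its confinement assessment is a day earlier: "11-dehydro-thromboxane B2 (11-DTX-B2) in 24-hour urine at baseline, Day 5, Day 30 Visit, Day 60 Visit, and Day 90 Visit".

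Protocol 3.2, secondary objective 6, defines the endpoints on the same days. For sICAM-1 it has: "Soluble inter-cellular adhesion molecule-1 (sICAM-1) in serum on Day 6, at Visit 2, Visit 3, and Visit 4". Its entry for the blood counts names the same day and visits.

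**The concern.** The analysis sentence and the endpoint list disagree on the day of the short-term comparison. Three of the parameters (sICAM-1, WBC, platelets) are not sampled on Day 5, so a Day 5 model cannot be fitted for them. For blood pressure a Day 5 value does exist, because vital signs are taken daily in confinement. A Day 5 model would therefore run without error, but on a day that is not the defined endpoint.

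What is at stake is the one cardiovascular comparison made while product use is controlled stick by stick and almost nobody is expected to leave the per-protocol set. For sICAM-1, WBC and platelets, the literal text leaves Day 90 as the only modelled comparison. That comparison is made in a per-protocol set which, in the CHTP 1.2 arm, is selected by cigarette use after randomization. Leaving the day open for blood pressure also allows the choice between Day 5 and Day 6 to be made after the data are seen, for endpoints without multiplicity adjustment (SAP 12.1.8).

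**Working it through.** **Step 1: scheduled days against ANCOVA days.** SAP 12.5.2.6 lists 20 parameters. Sorted by their first post-baseline assessment:

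| Confinement endpoint | Parameters | Count |
|---|---|---|
| Day 5 | 11-DTX-B2 | 1 |
| Day 6 | systolic BP, diastolic BP, sICAM-1, WBC, platelets | 5 |
| None | hs-CRP, glucose, MPO, LDL, HDL, TG, TC, fibrinogen, homocysteine, HbA1c, Apo A1, Apo B, weight, waist circumference | 14 |

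So 1 + 5 = 6 parameters have a confinement endpoint. The Day 5 rule fits one of them and misses five. The 14 others are unaffected.

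**Step 2: is there any Day 5 value to model?**

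- *sICAM-1, WBC, platelets: no.* In Protocol Table 13 (Day 5), the fasting risk-endpoint draw covers 8-epi-PGF2α, PGF2α, 4-HNE and TAC only. Table 14 (Day 6) has the draw: "Clinical laboratory parameters* (hematology, clinical chemistry), cardiovascular clinical risk endpoint: sICAM-1". Protocol Table A1 agrees: sICAM-1 on Days -1, 6, 31, 61 and 91; hematology at Screening and on Days -1, 6, 30, 60 and 91. SAP Table 14 has one shared row for blood laboratory and risk endpoints that names both Day 5 and Day 6. That row applies only where relevant, and the oxidative-stress draw accounts for its Day 5 entry.
- *Blood pressure: yes, but not as the endpoint.* Vital signs are taken on every confinement day. Footnote a to Protocol Table A1 limits the risk-marker analysis of blood pressure to Day -1, Day 6 and Visits 2 to 4.

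**Step 3: was Day 5 chosen on purpose?** SAP section 9, which lists departures from the protocol, records no change of day for these endpoints. Elsewhere the SAP names Day 6 when it means Day 6: the spirometry (12.5.2.4) and CYP2A6 (12.5.3.2) comparisons both do so. Day 5 here looks like a slip.

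**Step 4: does the bracketed qualifier repair it?** There are two readings.

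- It limits Day 5 to endpoints that have a Day 5 value. Then sICAM-1, WBC and platelets have no confinement model. Blood pressure goes to the Day 5 vital sign, or to no model if only the section's own list counts.
- It is shorthand for the end of confinement. Then the stated day is wrong for five of six parameters.

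Neither reading specifies a Day 6 model. The later wording about showing results by time point only formats output from models already limited to Day 5 and Day 90.

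**Step 5: relative precision of the two comparisons.** SAP section 8 plans 80 v 40 subjects, minimal per-protocol exclusions in confinement, and at least 50% of the CHTP 1.2 arm remaining at Day 90. For equal SD, the standard error is proportional to √(1/n₁ + 1/n₂):

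- Confinement, 80 v 40: √(1/80 + 1/40) = 0.194
- Day 90 at the 50% floor, 40 v 40: √(1/40 + 1/40) = 0.224; 0.194/0.224 = 0.866, about 13% smaller in confinement
- Day 90 if 60 of 80 remain, 60 v 40: √(1/60 + 1/40) = 0.204; 0.194/0.204 = 0.95, about 5% smaller in confinement

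**The case against.** The strongest reply accepts the mismatch and disputes its weight.

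- **The protocol never promised a Day 6 test.** Objective 6 is to monitor these endpoints, Protocol 12.5.3 plans descriptive summaries, and the hypothesis test in 12.4.4 concerns biomarkers of exposure. The ANCOVA is a SAP addition with no confirmatory role. This stands, and it limits the importance.
- **Day 6 data are still reported.** Values and changes by arm and time point, mean profiles with 95% CIs, and the safety tables all remain. This stands too: the loss is one baseline-adjusted contrast per endpoint, not the data.
- **The expected signal is later for some endpoints.** Protocol 4.2 cites short-term evidence (5 days or 1 week) for 11-DTX-B2, and 1 to 3 months of cessation for sICAM-1 and WBC. This is fair as to where an effect is likely. It does not make a model on an unsampled day executable.
- **The blood pressure error is less certain.** The section lists no Day 5 blood pressure, so the vital sign need not be used, and the shift would be one day. This is correct. The clear cases of no possible model are sICAM-1, WBC and platelets; for blood pressure the day is ambiguous.
- **The standard-error figure does not measure the defect.** It compares two exposure durations and uses the floor of the retention assumption. It should be read only as the relative precision of the two comparisons.
- **The table shells are in a separate document and might show Day 6.** That is possible, but the SAP is the governing specification and does not provide for it.

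**Conclusion.** The concern holds. As written, the rule gives no confinement ANCOVA for three endpoints (sICAM-1, WBC, platelets). For two more (systolic and diastolic blood pressure) it gives none, or one on a day that is not the endpoint. That is five of the six cardiovascular parameters with a confinement endpoint; only 11-DTX-B2 is right. No other place in either document corrects the sentence.

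The consequence is moderate. The endpoints are secondary and unadjusted for multiplicity, descriptive Day 6 results remain, and the primary analysis is unaffected. The precision advantage of the confinement comparison is about 13% in standard error at the 50% retention floor and about 5% if 60 of 80 remain. Both figures assume equal SD and no losses in confinement or in the CC arm. The change should be made, but the trial's main conclusions do not depend on it.

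**What to change.** Replace the sentence in SAP 12.5.2.6 with:

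> An ANCOVA will be fitted on Day 5 for 11-DTX-B2; on Day 6 for systolic and diastolic blood pressure, sICAM-1, WBC and platelets; and at the Day 90 Visit for all endpoints.

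Day 6 up to discharge falls within Period 1 (SAP Table 7), so the existing Period 1 per-protocol set applies. The table shell for 15.2.4.28 should be checked for a Day 6 panel. The cost is one SAP sentence. No new data or visits are needed, and the days match those already defined in Protocol 3.2 and in the SAP endpoint list.
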